4. SELECTION AND ENROLLMENT OF PARTICIPANTS

4.1 Inclusion Criteria

Participants must meet all of the inclusion criteria to participate in this study.

Inclusion Criteria Include:

1. Fulfill 2010 Fibromyalgia Diagnostic Criteria(1)
2. Age 18-70 years old
3. Right-handed(96)
4. Agree to and able to have at least three fMRI scan sessions as well as rTMS(97) sessions
5. Willingness to suspend use of analgesic drugs or cough suppressants for 24 hours prior to the scans
6. Willingness to suspend use of antidepressant drugs for 2 weeks prior to the scans (6 weeks for fluoxetine)
7. Proficiency in English sufficient to complete questionnaires / follow instructions during fMRI assessments
8. US Citizen or resident able to receive payment legally
9. Low-Moderate Hypnotizability in the Hypnotic Induction Profile (score of 0-8)(98)
10. Normal color vision
11. Not pregnant and if participant is of childbearing potential, must agree to use adequate contraception prior to study and for the duration of study participation.

We will enroll 18-70 year old right-handed(96)*, male and female participants with a confirmed diagnosis of Fibromyalgia Syndrome (FMS)(1), low-moderate hypnotizability (a HIP score from 0-8)(98), no contraindications to rTMS(97) or MRI(89) and no other disease causing pain.

**Right-hand dominant ambidextrous participants are included.*

Required Diagnostics: Individuals will meet gold-standard criteria for FMS. The confirmation of diagnosis involves meeting the gold-standard criteria for the diagnosis of FMS, the American College of Rheumatology Preliminary Diagnostic Criteria for Fibromyalgia(1). Participants will meet criteria within 2 months prior to the date of first scanning session. Individuals will have a normal CBC and inflammatory panel. Participants will have to have labs drawn within 1 year.

Prior Therapy: Participants cannot be taking psychoactive medications (antidepressants, opiates) during the rTMS sessions due to increased risk of seizure(99) and/or manipulation of the participant's cortical excitability(100). We will not require participants to have taken any prior medications/therapies for FMS to be included in this study. Participants will have to have the ability to understand study procedures and to comply with them for the entire length of the study.

Participants cannot have been exposed to TMS in any way prior to enrolling in this study because it will affect blinding(86).

4.2 Exclusion Criteria

All candidates meeting any of the exclusion criteria at baseline will be excluded from study participation.

Exclusion Criteria Include:

1. A medical condition that would contraindicate the use of rTMS (101)
2. Metal implants that would contraindicate MRI (like ferromagnetic metal in their body) or contraindicate rTMS (metal in or near the head) (101)
3. Pregnancy (99)
4. Any significant neurologic disease, including dementia, Parkinson's or Huntington's disease, brain tumor, seizure disorder, subdural hematoma, multiple sclerosis, history of significant head trauma (101)
5. Current use of an antidepressant medication for depression(102)
6. Previous exposure to any rTMS approach (86)
7. High Hypnotizability in the Hypnotic Induction Profile (score of 9-10)(98)
8. High risk for opiate withdrawal due to excessive use as determined on the Opiate Risk Tool if the participant is already on opiates (103).

Participant cannot be diagnosed with any condition expected to change their morbidity or mortality within 6 months of the start of the study such that appropriate diagnosis, treatment, or follow-up for the trial will be affected. Participants with known malignancy will be excluded from this study if the malignancy is causing pain that will interfere with the study or if there is any known/potential neurological involvement. All drug and alcohol dependence will be excluded from this study except nicotine dependence will be allowed. Inability or unwillingness of individual to give written informed consent will exclude that individual from participating.

The effects of rTMS on the developing human fetus are unknown(104). We will not be enrolling pregnant women to this study. Women of childbearing potential must agree to use adequate contraception (hormonal / barrier method of birth control or abstinence) prior to study entry and for the duration of study participation. Females of childbearing-age, will have a pregnancy test prior to receiving each rTMS stimulation session. Should a woman become pregnant or suspects she is pregnant while participating in this study, she should inform study staff.

Taking psychoactive medication during the rTMS portion of the study is contraindicated due to potential for increase of seizure risk(99) and change in cortical excitability(100). Participants taking antidepressants for depression will be excluded. Participants taking antidepressant medication for FMS will be offered the option of a wash-out (2 weeks prior to first scan session except fluoxetine is 5 weeks due to the half-lives of these medications). Patients taking

antidepressants at the time of consent will be excluded from the study. No investigational treatments will be allowed during this study.

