6. STUDY PROCEDURES

6.1 Schedule of Evaluations

Assessment	Redcap Screening: Online	Baseline, Enrollment, Randomization: Visit 1 (Day 0)	TMS Target Scan Day	Hypnotic Stroop Scan Day	Hypnotic Analgesia Scan Day
Online Consent	X				
Informed Consent Form 1 (Screening)		X			
Demographics	X				
Screening Forms	X	X	X	X	X
Medical History	X	X			
Current Medications	X	X		X	X
Informed Consent 2 (Full)		X			
Blood Chemistries		X			
Urine Analysis				X	X
Inclusion/Exclusion Criteria	X	X			
Enrollment/Randomization		X			
Stimulation Log				X	X
Concomitant Medications		X		X	X
Adverse Events		X	X	X	X
HIP/SOARS		X		X	X
HIS				X	X
Pain Induction					X
Stroop Task				X	

Table 2: The table includes the schedule for all of the assessments.

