The Mini-International Neuropsychiatric Interview (M.I.N.I.): The MINI is a short structured diagnostic interview, developed jointly by psychiatrists and clinicians for Diagnostic and Statistical Manual of Mental Disorders-IV (DSM-IV) and International Classification of Diseases (ICD) 10th revision psychiatric disorders. The *M.I.N.I.* was designed to meet the need for a short but accurate structured psychiatric interview for multicenter clinical trials and epidemiology studies and to be used as a first step in outcome tracking in non-research clinical settings(115).

Transcranial Magnetic Stimulation Adult Safety Screen (TASS): This is a participant self-report instrument. Participants will fill out a TASS questionnaire to determine risk of seizure related to rTMS(88). Any identified seizure risk will disqualify the participant. This assessment is utilized in order to minimize the risk of seizure induction with rTMS.

MRI Safety Screening Form: This is a participant self-report instrument. Participant will fill out a MRI Safety Screening Form to determine if the participant is safe to receive an MRI. We will utilize this screening tool to make sure that the participant has no contraindications for MRI that would exclude the participant from participating(89).

Edinburgh Handedness Inventory: This is a clinician-administered instrument. Participants must be right-handed to participate in this study(96). It is standard to restrict rTMS studies to right-handed individuals only due to variability in hemispheric dominance of left-handed individuals.

The Opioid Risk Tool (ORT): This is a brief, self-report screening tool designed for use with adult patients in primary care settings to assess risk for opioid abuse among individuals prescribed opioids for treatment of chronic pain. Patients categorized as high-risk are at increased likelihood of future abusive drug-related behavior (103).

The Brief Pain Inventory: The BPI measures both the intensity of pain (sensory dimension) and interference of pain in the patient's life (reactive dimension). It also queries the patient about pain

relief, pain quality, and patient perception of the cause of pain(116). The BPI has been validated in FMS(117).

Short-Form McGill Pain Questionnaire (SF-MPQ): The SF-MPQ is a shortened version of of the MPQ providing information pertaining to the sensory, affective, and evaluative dimensions of the pain experience.

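### Exclusion 8 names risk of opiate withdrawal but decides it by a tool the protocol describes as a screen for opioid abuse, so a prescribed-opioid user at risk of withdrawal can pass it

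*Combined protocol and SAP*

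**What the plan says.** All references are to the combined protocol and SAP; the separate SAP does not deal with eligibility.

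- **The criterion (section 4.2, exclusion 8):** "High risk for opiate withdrawal due to excessive use as determined on the Opiate Risk Tool if the participant is already on opiates". No cut-off, dose or duration is given.
- **The tool (section 6.2.1):** a brief self-report instrument "to assess risk for opioid abuse among individuals prescribed opioids for treatment of chronic pain". On its top category: "Patients categorized as high-risk are at increased likelihood of future abusive drug-related behavior". The two sections spell the tool's name differently but cite the same reference (103), so I treat it as one instrument.
- **Opioid users may enrol:** exclusion 8 applies only to people already taking opiates and removes only those at high risk. The Précis asks that participants be off opiates on the day of rTMS.
- **Those who enrol must stop:** inclusion 5 (section 4.1) requires "Willingness to suspend use of analgesic drugs or cough suppressants for 24 hours prior to the scans". Prior Therapy in the same section adds "Participants cannot be taking psychoactive medications (antidepressants, opiates) during the rTMS sessions". Section 5.3.3 goes furthest and bars opiates on both the day before and the day of scanner sessions.
- **Other screening provisions:** section 4.2 also states "All drug and alcohol dependence will be excluded from this study except nicotine dependence will be allowed". Section 6.2.1 includes the M.I.N.I. ("The MINI is a short structured diagnostic interview"). The section 6.1 schedule has a row for "Current Medications", marked at online screening, Visit 1 and both rTMS scan days.

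**The concern.** The hazard that exclusion 8 names and the quantity its instrument is said to measure are different things. Risk of withdrawal when opioids are held depends on what the person is taking now. The protocol's account of the tool concerns the chance of later misuse. Because the criterion is settled by the tool, its result decides eligibility on this point. Someone on long-term prescribed opioids, physically dependent but at low risk of misuse, could be passed by the one criterion written to protect them.

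What is at stake is participant safety. Meeting such people is foreseeable: section 4.3 recruits from a pain clinic among others, and section 2.1 discusses long-term opioid use in fibromyalgia.

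**Working it through.** The main check is a comparison of texts. The only arithmetic concerns how long opioids would be held.

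**1. Criterion against tool.**

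| | Exclusion 8 (4.2) | Tool as described (6.2.1) |
|---|---|---|
| Risk | Opiate withdrawal | Opioid abuse |
| Basis | Excessive current use | Brief self-report |
| Meaning of high risk | Should not be taken off opioids for the study | More likely to misuse drugs in future |

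The last entry in the middle column is my reading of the criterion's purpose. The documents do not say that the tool records dose, duration, physical dependence or withdrawal. A pass on exclusion 8 therefore does not establish low withdrawal risk.

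**2. Provisions that act before opioids are held.**

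- Drug-dependence exclusion (4.2): dependence is not defined, and the text does not say whether physical dependence on prescribed opioids counts.
- M.I.N.I. (6.2.1): a psychiatric diagnostic interview; its modules are not listed and no link to withdrawal is stated.
- Medication review (6.1): a row title only, with no decision rule for opioids.
- Inclusion 5 (4.1): someone unwilling to suspend analgesics is not eligible. This is self-selection, not assessment.

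Each may remove some at-risk people. None is described as assessing withdrawal risk.

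**3. Provisions that act after opioids are held.** Section 9.1 allows exclusion if the washout cannot be tolerated, referral to a clinician for distress, and round-the-clock cover, all framed around antidepressants. The scan-day medication form (6.2.2), adverse event collection (7.4) and withdrawal by the investigator (8) also come after the stop.

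**4. Length of the hold under section 5.3.3.** For a scanner day d, the held days are d−1 and d. The unbroken hold is the longest run of consecutive held days. If exactly one free day lies between two scanner days, that free day is itself a day before, so the two holds join.

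Two scanner days (the two rTMS days only, or the target scan done on the same day as Visit 3, which the Précis allows):

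| Free days between | Held days | Longest run |
|---|---|---|
| 0 | d−1, d, d+1 | 3 |
| 1 | d−1, d, d+1, d+2 | 4 |
| 2 or more | two separate pairs | 2 |

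Three scanner days (a separate target scan also counts):

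| Free days in the two gaps | Longest run |
|---|---|
| 0, 0 | 4 |
| 0, 1 or 1, 0 | 5 |
| 1, 1 | 6 |
| 0, 2+ or 2+, 0 | 3 |
| 1, 2+ or 2+, 1 | 4 |
| 2+, 2+ | 2 |

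Visit spacing is not stated, so the result is a range: 2 to 4 calendar days with two scanner days, and 2 to 6 with three. The optional spectroscopy visit is not counted.

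**5. Which count applies.** The Précis (three required scan session days) and section 5.4 (three mandatory scanner visits) support counting the target scan. Section 3 speaks of two scanner session days with rTMS on both, and section 6.2.2 describes the medication washout form only for the two pre-rTMS assessments. The scope of section 5.3.3 is therefore open.

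**The case against.** The strongest reply accepts the mismatch in wording and disputes its consequence.

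**The tool's items are not visible.** The protocol gives only a short summary, and its silence on dose does not show how a heavy user would score. That stands, and it limits the claim: an at-risk user can pass, not will pass. It does not rescue the criterion, because the protocol offers no reason to think the score tracks withdrawal.

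**There are several other filters.** Besides those listed above, there is a second consent discussion of procedure risks (6.2.1), direct contact with the investigator and immediate care for adverse events (7.4), and freedom to leave at any time (8). Together they make an unnoticed heavy user less likely. That also stands. None of them is described as judging withdrawal risk before the stop.

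**The exposure may be small.** The number of opioid users at risk is not given and could be zero. The medication form may already record dose. Both points are fair, and they are why the impact is put no higher than modest.

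**The hold may be short.** A reader might take 6 days as the plan's plain upper limit, or infer something longer from section 9.1, which announces a washout for all psychoactive drugs. The documents support neither as a simple statement. Six days needs a separate target scan to count and one free day in each gap. Section 9.1 gives lengths only for antidepressants and says that only people taking those for pain are washed out, so whether it reaches opioids is unclear.

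**Conclusion.** The point holds. Exclusion 8 is wrong as written: the rule it states does not assess the hazard it names. Identifying an at-risk person before opioids are held is left to provisions not described as doing so.

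The safety impact is modest. For anyone who passes every filter, the longest unbroken hold is 2 to 4 calendar days if only the two rTMS scanner days count, and up to 6 only on the conditions given above. This rests on reading section 5.3.3 by calendar day and on visit spacing being unstated.

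A reader might go further and infer that participants will come to harm, or that withdrawal would distort the pain results. The documents give no count of opioid users or of those at risk. Both arms follow the same medication rules, and no bias in the active-sham comparison is shown.

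**What to change.** Reword exclusion 8 so that a study clinician judges withdrawal risk from current opioid use (drug, dose, frequency, duration). Record this with the medication review already scheduled at online screening and Visit 1, and make the judgement before any opioid is held. The study clinicians can set a threshold if they want a uniform rule. Keep the Opioid Risk Tool, if wanted, as a separate criterion named for abuse risk.

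Optional clarifications: say whether the section 9.1 washout covers opioids and whether the target scan counts under section 5.3.3. Use one off-opioid rule in the Précis and sections 4.1 and 5.3.3; following 5.3.3 already satisfies the other two.

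The cost is one eligibility sentence and no new visit. The medication form may need added fields, since the schedule shows only a row title. Some long-term opioid users, number unknown, may be screened out. Clinical judgement replaces a standardised score unless a threshold is set.

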Washout Period: Due to risk of seizure (97), we will implement a washout period for all psychoactive medications (99, 102) that will be implemented prior to the first scan session and continued through to the second scan session day. For all antidepressant medications other than fluoxetine, there will be a 2-week washout. For fluoxetine, there will be a 5-week washout period(102). The reason for 2 weeks for all antidepressants except fluoxetine (5 weeks) has to do with the half-life of the antidepressants(102). We will only washout those individuals who are taking antidepressants for pain. We will not washout antidepressant prescribed for depression due to the risk of exacerbating depression. If participants find this portion of the study intolerable from a mood/pain standpoint, we will exclude the participant prior to the scanner portion of the study and this participant will be considered a screen failure and replaced.

The safety monitoring protocol for the medication wash-out has been successfully employed in two former randomized controlled trials for suicide prevention in which the Chair of the Independent Monitoring Committee was a mentor (DOD/MSRC [W81XWH-10-2-0178] and NIH

[K23MH093490]). All procedures will be closely supervised by the study PIs and on-site Independent Monitoring Committee, [name] (Mood Disorders Expert). Suicide risk assessment will be conducted using empirically-established risk categorizations (minimal, mild, moderate, severe, imminent) to routinize clinical decision-making and emergency referral procedures for suicidal behaviors. This study will utilize a comprehensive, in-built infrastructure and set of standard operating procedures that support safe conduct of the current trial. Based on evidence-based best practices in standardized risk assessment and management, subjects at imminent risk will be referred for immediate hospitalization. Proposed procedures have been used in previous IRB-approved proposals consistent with DSMP protocols employed by Drs. [name].

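### Antidepressant washout is decided only by why the drug is taken, so a person in a current major depressive episode whose drug is classed as for fibromyalgia or pain may be offered it

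*Combined protocol and SAP*

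**What the plan says.** **The washout rule.** Exclusion criterion 5 in section 4.2 reads "Current use of an antidepressant medication for depression". The closing text of 4.2 excludes people who take antidepressants for depression and then states: "Participants taking antidepressant medication for FMS will be offered the option of a wash-out". Section 9.1 (Washout Period) gives the same split: "We will only washout those individuals who are taking antidepressants for pain", and "We will not washout antidepressant prescribed for depression due to the risk of exacerbating depression".

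**Screening.** Section 6.2.1 lists the M.I.N.I. among the screening tools. It also lists the clinician-administered Antidepressant Treatment Response Questionnaire (ATRQ), which covers antidepressant use in both depression and pain.

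**Duration.** Washout is "implemented prior to the first scan session and continued through to the second scan session day". Sections 4.2 and 9.1 set 2 weeks for antidepressants other than fluoxetine. Section 9.1 adds "For fluoxetine, there will be a 5-week washout period", and 4.2 also gives 5 weeks. Inclusion criterion 6 in section 4.1 asks for willingness to stop for 2 weeks, or 6 weeks for fluoxetine.

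**The consent sentence.** Directly after the washout offer, 4.2 says that patients taking "antidepressants at the time of consent will be excluded from the study". Section 6.2.1 describes three consent processes and 4.2 does not say which one is meant.

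**The concern.** Section 9.1 declines to wash out drugs prescribed for depression because stopping them may make the depression worse. That danger comes from the person's mood state as much as from the reason written against the drug. Someone who is in a current episode and takes an antidepressant that is classed as for FMS or pain raises the same concern, yet falls on the washout side of the rule.

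Washout is also the step for which the protocol builds its suicide-risk programme. The trial is mechanistic, with no follow-up beyond the scan sessions (section 3), so the drug is stopped for the sake of the scans and stimulation safety, not to treat that person. A rule on who should not start washout is therefore worth having, and the information it needs is already collected.

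**Working it through.** No arithmetic drives the main point. The check sets the passages side by side.

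**1. What the rule does in each case** (criterion 5 and closing text of 4.2; Washout Period in 9.1)

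| Drug classed as for | Current episode on M.I.N.I. | No current episode |
|---|---|---|
| Depression | Excluded | Excluded |
| Depression and FMS or pain | Can be read as excluded (criterion 5) | Can be read as excluded (criterion 5) |
| FMS or pain only | **Washout offered** | Washout offered |

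The two columns are identical, so the M.I.N.I. result changes nothing. The gap is the cell in bold.

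**2. Whether another passage closes that cell**

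- In 6.2.1 several tools carry a stated consequence: the hypnotizability score range, the TMS safety screen, handedness and colour vision. The M.I.N.I. entry carries none.
- The ATRQ entry gives washout or exclusion as the options, and its stated ground is seizure risk, not mood.
- Among psychiatric findings, 4.2 names drug and alcohol dependence as an exclusion but no mood disorder.
- The general clause in 4.2, "Participant cannot be diagnosed with any condition expected to change their morbidity or mortality within 6 months of the start of the study", does not name depression and applies only where diagnosis, treatment or follow-up for the trial would be affected.
- Section 8 lets the Principal Investigator withdraw someone for safety. That is discretionary and sets no entry threshold.

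**3. What the safeguards in 9.1 do.** Next-of-kin permission and referral resources are reviewed before enrollment, and risk procedures are reviewed as washout begins. After that come supervision by the investigators and a mood-disorders expert, 24-hour cover and weekly SSI-C calls. The participant is excluded if washout proves intolerable. The one score with a stated action is an SSI-C above 6. Weekly calls over 2 weeks give about 2 calls before the first scan; over 5 weeks for fluoxetine, about 5. No score is stated as required before the drug is stopped.

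**4. Fluoxetine.** 5 weeks × 7 = 35 days (4.2, 9.1) and 6 weeks × 7 = 42 days (4.1). The difference is 42 − 35 = 7 days.

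**5. The consent sentence.** Suppose it meant a consent given before washout. No antidepressant user could then be washed out. Inclusion criterion 6, the ATRQ text, the washout part of 9.1 and the washout form in 6.2.2 would have no one to apply to. If it means the full consent after washout, all of them work. That reading fits the Précis, where consent for imaging and rTMS follows once criteria are met, and 9.1, where a participant who cannot tolerate washout counts as a screen failure. The schedule in 6.1 does not settle the matter. It puts both in-person consents at Visit 1, but it also puts randomization there, which 6.2.2 places just before stimulation.

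**The case against.** The best case for the plan is that the gap is narrow and well guarded. Use for depression is excluded in three places. A clinician checks indication with the ATRQ, and mixed use can be read as excluded. The M.I.N.I. is one of the tools used to screen participants, and a Screening Complete Form in 6.2.1 lists the questionnaires for the eligibility check. Washout is offered, not imposed. Section 9.1 also relies on standard operating procedures, a checklist and a decision tree that are not in the text available here. All of this stands, and it limits the finding to a missing rule in the visible text. It does not supply the rule: no visible passage says that a current episode bars washout.

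Three stronger readings are tempting, and the documents do not support them.

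- A reader might infer that the plan directs staff to wash out depressed people. It does not. An investigator may decline such a person on clinical judgement; the protocol simply does not require it.
- A reader might infer that the consent sentence cancels the washout offer. As shown above, that would leave four other parts of the protocol without effect, so the sentence is loosely worded rather than contradictory.
- A reader might infer that section 5.3.3, which bars antidepressants on the day before and the day of scanning, shortens the washout. It is a general ban on CNS-active drugs around the scans and leaves the longer period in force.

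The fluoxetine difference should not be overstated either. Criterion 6 concerns willingness, so a person 35 to 41 days off the drug who had been willing to stop for 6 weeks does not fail it. The two stated periods still disagree.

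**Conclusion.** The main point holds. In the visible text, washout depends on the reason for the drug and the participant's agreement, and a current major depressive episode on the M.I.N.I. does not bar it. The safeguards in 9.1 manage the risk without saying who should not start. This is a participant-safety rule that should be added; the existing mitigation keeps it from being more serious than that.

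Its size cannot be given as a number of people. The documents state neither the share of participants who take an antidepressant for FMS or pain nor the share of those in a current episode. The conclusion rests on two assumptions: that the M.I.N.I. as administered yields a result for a current major depressive episode, and that the procedures not available here contain no such bar.

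The fluoxetine period is a real inconsistency of 7 days. The consent sentence is an editorial matter.

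**What to change.** **Main change.** Add to 4.2 and 9.1: *Antidepressant users who meet M.I.N.I. criteria for a current major depressive episode are excluded and will not be washed out, whatever the indication; the M.I.N.I. result is recorded before any drug is stopped.* Participants who take no antidepressant are unaffected.

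**Fluoxetine.** Change inclusion criterion 6 from 6 to 5 weeks. Five weeks is already stated twice with a half-life rationale, and adopting 6 would lengthen the time off the drug.

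**Consent sentence.** Replace it in 4.2 with: *Participants who have not completed the required washout before the first scan session will be excluded before randomization.* The exclusion should end there. Randomization comes immediately before stimulation (6.2.2), so a rule that removed people who resumed the drug before the second scan day would drop randomized participants, against the as-randomized comparison in 9.4. Record a return to the drug after randomization as a protocol deviation, withhold any further stimulation on safety grounds, and keep the participant in the as-randomized analysis.

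**Cost.** Wording in 4.1, 4.2 and 9.1 and one case report form field, with no new instrument or visit. Some antidepressant users with current depression will not be enrolled; how many cannot be computed from the documents.
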